10.0 Procedures Involved

10.1 *Provide a description of **all research procedures or activities** being performed and when they are performed once a subject is screened and determined to be eligible. Provide as much detail as possible.*

NOTE: This should serve as a blueprint for your study and include enough detail so that another investigator could pick up your protocol and replicate the research. For studies that have multiple or complex visits or procedures, consider the addition of a schedule of events table in in your response.

Response:

Following informed consent, in order to rule-out sleep apnea as a confounder, all eligible participants will be offered screening for sleep apnea with the ApneaLink Plus for one night. Following a negative screen for sleep apnea, demographics, diagnoses, treatments, comorbidities, etc. will be extracted from the Electronic Health Record (EHR) using the Medical Record Review Questionnaire (to verify certain self-report data); beliefs about sleep will be determined by Dysfunctional Beliefs and Attitudes about Sleep; mood, anxiety and depression will be measured with Hospital Anxiety and Depression Scale; pain and quality of life will be determined by Functional Assessment of Cancer Therapy-G; sleep quality will be measured with Pittsburgh Sleep Quality Index; daily sleep will be assessed with 7-day sleep diary; objective sleep will be evaluated with 7-day actigraph; fatigue will be assessed with Profile of Mood States; and daytime sleepiness will be determined by the Epworth Sleepiness Scale (Johns 1991).

One week, after baseline assessments, each participant will be randomized by the biostatistician. Participants will then be scheduled for either the brief behavioral therapy for insomnia (BBTI) session (experiment) or the healthy eating program (HEP) session (control). Each intervention is approximately 45-minutes and will be delivered in the clinical setting, online teaching or home.

At the end of the interventions, each participant will be provided weekly sleep diaries to complete for 2-weeks and arrange for 2-follow up telephone calls using the Telephone Follow Up Script (attached). Each telephone contact will begin by reminding participants that their participation is voluntary and they may skip items they wish. Telephone

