contacts are not recorded, but the research assistant will orally ask the participant to respond to the questions in the Telephone Follow Up Script and record responses as described in 10.2. Study packets with questionnaires will be repeated approximately one-month, 3-months and 12-months after the intervention. Patient Evaluation Questionnaire will be administered 1-month and at end of study. Following the one-month data collection, the interventionist will contact participants to provide feedback on sleep diary data. In addition, two REDCap emails at 6-months and 9-months from the intervention will be sent to ensure patient safety and encourage participant retention. The emails will ask the participants to answer a safety question we currently ask at each previous data collection with a "Yes" or "No" answer: Do you find that your sleepiness is bad enough that you are at risk of falling asleep while driving or doing something hazardous or harmful? Additionally, we will ask 2 questions from the Sleep Diary about their sleep: Please rate over the past week: Restful sleep 0-4 (4=excellent) and Sleep quality 0-4 (4=excellent).

10.2 Describe what data will be collected.

NOTE: For studies with multiple data collection points or long-term follow up, consider the addition of a schedule or table in your response.

Response:

Data include apnea/hypopnea index, movement (i.e. actigraphs), self-report sleep diaries and sleep, mood and quality of life questionnaires. Two-semi-structured telephone interviews will be conducted. For each interview, the data will be the participant's oral responses to the questions of the interview instruments as recorded in the research assistant's handwritten notes.

Table 3. Study Variables, Measures, and Time Frames

Variable	Measure	Pr e	1- Mon th	3- Mont hs	6- Mont hs	9- Mont hs	12- Mont hs
Predisposing factors Sleep history Age, sex, race/ethnicity	Holland Sleep Disorders Questionnaire /ApneaLink Plus Medical Record Review Questionnaire	X X					
Precipitating factors Cancer stage/treatment	Medical Record Review Questionnaire	X					

Alcohol/nicotine/caffeine Comorbidities Medications							
Perpetuating factors Beliefs about sleep	Dysfunctional Beliefs and Attitudes about Sleep	X	X	X			X
Neurocognitive factors Symptoms: depression, anxiety and pain	Hospital Anxiety and Depression Scale (anxiety and depression), Functional Assessment of Cancer Therapy (pain)	X X	X X	X X			X X

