Data review includes eligibility, referral for sleep apnea, referral for low oxygen during sleep, completion of data collection instruments, adherence to intervention, number of follow up phone calls accepted, and outcome measures of efficacy:

sleep, mood, functional status and quality of life. Daytime sleepiness will also be evaluated daily, but monitored weekly. Additionally, as previously mentioned, we are adding a 6 and 9 month follow up email to check on participants' safety. If participants report that they are excessively sleepy, we will provide recommendations to reduce sleepiness by telephone or email.

Because of the minimal to low risk associated with this protocol there are no life-threatening anticipated adverse events for this proposed research project. In the event of an unanticipated adverse event, such as disease-related patient death, it will be reported to and reviewed by the PI, SMC, and referring physician within seven days. Next, the IRBs at Roswell Park Comprehensive Cancer Center and the University at Buffalo as well as sponsoring agencies (NINR) will be notified within 15 days. A thorough investigation will be initiated, including review of the protocol to insure no undue exposure to risk occurred.

19.3 Describe any safety endpoints.

Response:

This low risk intervention may lead to emotional distress in participants who may become frustrated if insomnia does not improve. Anxiety and depression will be assessed at baseline, one, three and 12-months post-intervention. Scores greater than seven on either scale will be communicated to participants who will be encouraged to contact their health care provider for follow up care.

19.4 Describe how the safety information will be collected (e.g., with case report forms, at study visits, by telephone calls with participants).

Response:

The safety information will be collected with self-report surveys, during study visits and by telephone calls with participants.

19.5 Describe the frequency of safety data collection.

Response:

Safety data collection occurs at baseline, weekly then at 1-month, 3-months and 12 months post-intervention.

19.6 Describe who will review the safety data.

Response:

The PI, study coordinator, research assistant and members of the Safety Monitoring Committee.

19.7 Describe the frequency or periodicity of review of cumulative safety data.

Response:

Reviews of cumulative safety data will initially occur weekly, then biweekly and eventually monthly.

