19.8 Describe the statistical tests for analyzing the safety data to determine whether harm is occurring.

Response:

Hospital Anxiety and Depression Scale scores will be summarized.

19.9 Describe any conditions that trigger an immediate suspension of the research.

Response:

We do not anticipate any condition that would trigger an immediate suspension of the research.

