21.0 Risks to Subjects

21.1 *List the reasonably foreseeable risks, discomforts, hazards, or inconveniences to the subjects related to their participation in the research. Consider physical, psychological, social, legal, and economic risks. Include a description of the probability, magnitude, duration, and reversibility of the risks.*

NOTE: Breach of confidentiality is always a risk for identifiable subject data.

Response:

A reasonable foreseeable risk is excessive daytime sleepiness early in the study from having night-time sleep curtailed as part of the intervention. Daily sleep diaries provide daily daytime sleepiness measures and the PI and Study Coordinator will monitor for this risk. The known discomforts associated with this study include the possibility that participants may become upset thinking about some of the questions or topics in this study. If this occurs, the participant should notify the research assistant and will then be provided with an appropriate referral for assistance. The skin on the participant's wrist may become irritated by wearing the actigraph. If this occurs, the participant will be advised to remove the actigraph, apply a thin layer of Eurcerin lotion to the affected area and wear the actigraph on the opposite wrist.

All reasonable efforts will be used to protect the confidentiality of the participants' protected health information. Identifiable data is immediately de-identified and de-identified data is stored separately from identifiable data. The results of this research will be published. However, we will keep participants' names and other identifying information confidential.

21.2 *Describe procedures performed to lessen the probability or magnitude of risks, including procedures being performed to monitor subjects for safety.*

Response:

NA

21.3 *If applicable, indicate which procedures may have risks to the subjects that are currently unforeseeable.*

Response:

NA

21.4 *If applicable, indicate which research procedures may have risks to an embryo or fetus should the subject be or become pregnant.*

Response:

NA

21.5 *If applicable, describe risks to others who are not subjects.*

Response:

NA

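### Early daytime sleepiness, the harm that section 21.1 attributes to the intervention, is missing from the safety endpoints (19.3) and the safety analysis (19.8), and no by-arm summary of it is specified for the two weeks after the session

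*Combined protocol and SAP*

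**What the plan says.** All references are to the combined protocol and SAP.

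- **Risk (21.1).** "A reasonable foreseeable risk is excessive daytime sleepiness early in the study from having night-time sleep curtailed as part of the intervention". The same section names the data source: "Daily sleep diaries provide daily daytime sleepiness measures and the PI and Study Coordinator will monitor for this risk".
- **Diaries after the session (10.1).** After either session, "each participant will be provided weekly sleep diaries to complete for 2-weeks". Section 10.2 lists sleep diaries among the study data, but Table 3 has no column for weeks 1 and 2.
- **Monitoring (19.2, 19.5-19.7).** Sleepiness is evaluated daily and monitored weekly, and participants who report excessive sleepiness receive advice. Safety data are collected weekly at first. Cumulative safety data are reviewed by a group that includes the Safety Monitoring Committee, at intervals that start weekly and lengthen.
- **Safety endpoints (19.3).** The answer is limited to emotional distress: "Anxiety and depression will be assessed at baseline, one, three and 12-months post-intervention".
- **Safety analysis (19.8).** The prompt is "Describe the statistical tests for analyzing the safety data to determine whether harm is occurring". The full answer is "Hospital Anxiety and Depression Scale scores will be summarized".
- **Other sleepiness measures (10.1, Table 3).** "daytime sleepiness will be determined by the Epworth Sleepiness Scale", at baseline and at 1, 3 and 12 months. There is also a yes/no item on hazardous sleepiness, described as "a safety question we currently ask at each previous data collection" and repeated by email at 6 and 9 months.
- **Efficacy analysis (17.1).** ISI at 1 month is analysed by ANCOVA with a permutation test. Secondary outcomes are handled similarly but are not listed.

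**The concern.** The risk section and the safety-analysis section do not match. Section 21.1 identifies a specific harm, a mechanism (curtailed sleep) and a time (early). The sections that define safety endpoints and say how harm will be assessed cover only mood.

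The participants have insomnia, so sleepiness may be reported in either arm. Finding and advising sleepy individuals is a different task from estimating how much sleepiness BBTI adds over HEP. The randomized control arm makes that estimate possible, and diaries are issued to both arms for the relevant fortnight. If 19.8 is followed as written, the final safety account will summarize HADS and need not report the one harm that 21.1 links to the intervention's mechanism, in the period when it is most expected.

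**Working it through.** **Step 1. Does any section cover weeks 1-2 by arm?**

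- *19.3 and 19.8:* anxiety and depression only.
- *19.2, 19.5-19.7 and 21.1:* participant-level monitoring and cumulative review. No statistic is stated. The text does not say whether the cumulative review is by arm or pooled.
- *17.1:* the secondary-outcome sentence can reasonably be read to include Epworth, although neither the endpoints in 2.1 nor Hypothesis 1 names sleepiness. Its first post-session value is at about 1 month, after the early window.
- *Hazardous-sleepiness item (10.1):* no analysis is stated, and the text does not show it being asked in weeks 1-2.
- *21.2 (procedures to lessen or monitor risk):* answered as not applicable.

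No section specifies a by-arm summary of diary sleepiness in post-session weeks 1 and 2.

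**Step 2. Numbers per arm.** The plan gives no figure for sleepiness, so the available numbers come from its sample size for ISI (17.2: SD 4.8, difference 3, 90% power, two-sided 0.05).

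- Normal approximation: 2 × (1.96 + 1.2816)² × 4.8² / 3² = 53.8, so 54 per arm. The t-test version gives 54.8, so 55, as stated.
- Enrolment: 110 / (1 - 0.30) = 157.1, so 158, or 79 per arm, as stated in 5.1 and 17.2.

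The plan's figures reproduce. It does not say when the 30% loss occurs, so the number per arm in weeks 1-2 is assumed to lie between 55 and 79.

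**Step 3. Precision if diary sleepiness is reduced to a proportion.** The documents give no rates, so all of these are assumed. The 95% CI half-width is 1.96 × sqrt[p1(1-p1)/n + p2(1-p2)/n].

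| Assumed rates (arm 1 vs arm 2) | 79 per arm | 55 per arm |
|---|---|---|
| 5% vs 5% | 6.8 points | 8.1 points |
| 10% vs 10% | 9.4 | 11.2 |
| 20% vs 20% | 12.5 | 15.0 |
| 5% vs 20% | 10.0 | 12.0 |
| 20% vs 40% | 13.9 | 16.7 |

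Example, 5% vs 20% at 55 per arm: 1.96 × sqrt[(0.0475 + 0.16)/55] = 0.120. The first three rows assume no added harm; the last two show the widening when the arms differ. This simple interval is somewhat narrow at low rates: the Newcombe score interval at 5% in both arms gives 7.8 points (79) and 9.8 points (55).

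**Step 4. Precision if the diary item is treated as a continuous score.** Assume one value per participant per week. The half-width is t(0.975, 2n-2) × sqrt(2/n), which is 0.31 SD at 79 per arm and 0.38 SD at 55.

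**The case against.** The strongest reply is that most of the concern is already met. Sleepiness is looked at daily, monitored weekly, reviewed cumulatively with committee involvement, and acted on. From 1 month, Epworth is collected and probably compared by arm. The protocol describes itself as minimal to low risk, and what remains is one descriptive comparison over two weeks. That correctly limits the scope, but it does not supply the missing endpoint or summary.

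Three stronger readings are tempting, and the documents do not support them.

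- *Sleepiness is unmonitored.* Sections 19.2 and 21.1 say otherwise.
- *Monitoring cannot reveal a difference between arms.* The documents are silent on whether the cumulative review is by arm. The supportable statement is that no by-arm summary is specified.
- *Leaving the hazardous-sleepiness item unanalysed is part of the early gap.* The item is tied to data collections and to the 6- and 9-month emails, and is not shown to be asked in weeks 1-2. Tabulating it may be useful but would not cover the early window.

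Two practical objections also stand. Issuing diaries does not establish that they are returned and entered as analysable data; 10.2 counts sleep diaries as study data, but Table 3 does not schedule them in weeks 1-2. The diary form and telephone script are attachments not shown, so the sleepiness item, its scale and any early telephone question cannot be checked.

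**Conclusion.** The point holds as an inconsistency between 21.1 on one side and 19.3 and 19.8 on the other. The harm attributed to the intervention is neither a listed safety endpoint nor part of the stated safety analysis, and no by-arm summary is specified for the fortnight after the session.

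It affects the safety conclusion only; the primary comparison of ISI at 1 month is untouched. It is worth correcting because the comparison follows directly from the design and should be cheap.

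Its value should not be oversold. With intervals between about 7 and 17 points either side under the assumed rates, the trial could miss a difference of around 10 points. The summary would be an estimate, not a powered test. These figures rest on assumed event rates, on 55 to 79 diaries per arm, and on a diary item that can be dichotomised or scored.

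**What to change.** Reconcile 19.3 and 19.8 with 21.1:

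1. In 19.3, list daytime sleepiness as a safety endpoint.
2. In 19.8, add a descriptive by-arm summary of diary sleepiness in post-session weeks 1 and 2, on the diary's own item and scale, with the difference, 95% CI and number responding in each arm. If a cut-off is used, the investigators should define it in advance.
3. State that these tables go to the Safety Monitoring Committee and that a null difference is not evidence of no harm.
4. Optionally, add a by-arm count of Yes answers to the hazardous-sleepiness item at each contact where it is asked, noting that this does not address the early window.

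The cost is a few lines of text and a few tables, plus retrieval and entry of the week 1-2 diaries if that is not already planned. No change in sample size or participant management is needed. The limits are the wide intervals and the possibility that later answers reflect the advice given under 19.2 to participants who report sleepiness.

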20.0 Withdrawal of Subjects

N/A: This study is not enrolling subjects. This section does not apply.

*20.1 Describe **anticipated** circumstances under which subjects may be withdrawn from the research without their consent.*

Response:

Participants will be withdrawn from the research without their consent if they are unable to complete their responsibilities listed on the consent form or if they falsify responses.

20.2 Describe any procedures for orderly termination.

NOTE: Examples may include return of study drug, exit interview with clinician. Include whether additional follow up is recommended for safety reasons for physical or emotional health.

Response:

The participants that require early termination from the study will receive a telephone call alerting them to the termination and thanking them for their participation. If participants are not available via telephone, a letter notifying them of their termination will be mailed to their home address.

20.3 Describe procedures that will be followed when subjects withdraw from the research, including retention of already collected data, and partial withdrawal from procedures with continued data collection, as applicable.

Response:

It is conceivable that some participants may decide not to fully participate, for example, not participate in the intervention, but complete survey and actigraph data. Their data is still valuable. Data collection would continue and participants would receive appropriate compensation.

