9.0 Recruitment Methods

N/A: This is a records review only, and subjects will not be recruited. NOTE: If you select this option, please make sure that all records review procedures and inclusion/exclusion screening are adequately described in other sections.

9.1 Describe when, where, and how potential subjects will be recruited.

NOTE: Recruitment refers to how you are identifying potential participants and introducing them to the study. Include specific methods you will use (e.g. searching charts for specific ICD code numbers, Research Participant Groups, posted advertisements, etc.).

Response:

Recruitment flyers (attached) will be distributed to institutions/organizations in WNY where participants are likely to be encountered like Cancer centers, community centers, Senior centers, VFW posts, etc. Study recruiters will review clinic schedules and prescreen medical records for cancer diagnosis, stage of disease and last treatment date to highlight potentially eligible participants for clinic staff. Clinicians involved in medical management of cancer survivors and their staff, will identify potential eligible participants, briefly explain the study, and obtain agreement from potential participants to be contacted. The PI or Study Coordinator will then contact the eligible participant to obtain their affirmative response of their interest in participating and then arrange to meet each potential participant in the clinic or at their home, if preferred. Additionally, given the shelter-in-place situation and some previous patients had difficulty returning to the clinic for the face-to face intervention, we will now offer the option of verbal consent and online teaching.

The following Research Participants Groups will be added: Buffalo Research Registry, Research Match, and i2b2. For i2b2, following IRB approval, the Institute of Healthcare Informatics team will provide contact information for the eligible participants. The provider will be contacted for approval using the Physician Permission Letter (draft letter attached). If the provider does not object, patients will be contacted by mail (draft letter attached) and then by telephone.

9.2 *Describe how you will protect the privacy interests of prospective subjects during the recruitment process.*

NOTE: Privacy refers to an individual's right to control access to him or herself.

Response:

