11.0 Study Timelines

11.1 Describe the anticipated duration needed to enroll all study subjects.

Response:

The enrollment period is planned for 3 years.

11.2 Describe the duration of an individual subject's participation in the study. Include length of study visits, and overall study follow-up time.

Response:

One week of data collection at home by the participant. Randomization to an intervention involving one 45-minute individual session with two 30-minute telephone calls delivered 1- and 2-weeks after the intervention concluding with a 1-month, 3-month and 12-month follow up in person or by mail. Following the one-month data collection, the interventionist will contact participants to provide feedback on BBTI and PASS programs.

Participation will involve approximately 11-12 hours over a 13-month time period.

11.3 Describe the estimated duration for the investigators to complete this study (i.e. all data is collected and all analyses have been completed).

Response:

The estimated duration for the investigators to complete this study is 5 years.

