17.0 Data Management and Analysis

17.1 *Describe the data analysis plan, including any statistical procedures. This section applies to both quantitative and qualitative analysis.*

Response:

Specific Aim 1. The primary analyses involve the statistical assessment of Insomnia Severity Index (ISI) at 1 month and will be based on an analysis of covariance (ANCOVA) model. In taking this approach, we fit the dependent variable as a linear function of independent variables randomized treatment assignment, patient cancer type, the interaction between treatment assignment and cancer type, and baseline ISI level. Rather than utilizing the null distribution associated with the classic F-test for overall treatment differences within the ANCOVA framework, which is dependent on the validity of distributional assumptions, an exact permutation testing approach will be utilized. The randomization mechanism at work is a crucial component in this study in that it will be used to create the randomization distribution by which statistical significance will be determined. For more on this approach see Gail, Tan, and Piantadosi (1988)(120). Reported p-values will be obtained from the permutation distributions of the test statistics based on 10,000 Monte Carlo simulations. As additional analyses, subject covariates will be included as independent variables.

The interaction of treatment group and subject covariates may also be examined in a secondary fashion in order to identify possible differential effects of treatment. The analysis of secondary outcomes will proceed in a similar fashion. All statistical tests will be two-sided and tested at a 0.05 nominal significance level.

Specific Aim 2. Standard multiple regression will be used to determine predictors of efficacious response to BBTI. Standard diagnostic plots will be used to assess model fit and transformations of variables may be considered in order to meet statistical assumptions.

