experience, we expect a 30% drop out rate, thus a total of 158 patients will be enrolled into this study.

17.3 Describe any procedures that will be used for quality control of collected data.

Response:

Participants will receive detailed verbal and written instructions from the PI and study coordinator on how to wear the actiwatch, complete the sleep diaries and self-report questionnaires. Also provided will be how to contact the PI and study coordinator with questions. Reminders and prompts will be provided to participants to avoid unintentional missing data.

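### Read literally, 20.1 ends outcome collection for randomized participants who cannot complete study tasks, while 20.3 continues it only for those who choose to skip them

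*Combined protocol and SAP*

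**What the plan says.** Three short answers in section 20.0 govern who leaves the study and what is still collected.

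- 20.1 is mandatory and makes no exception after randomization: "Participants will be withdrawn from the research without their consent if they are unable to complete their responsibilities listed on the consent form". Falsified responses are the only other trigger.
- 20.2 says that people terminated early "will receive a telephone call alerting them to the termination and thanking them for their participation", or are sent a letter if they cannot be reached. It mentions no last outcome assessment.
- 20.3 accepts that "some participants may decide not to fully participate, for example, not participate in the intervention, but complete survey and actigraph data". It calls such data valuable and keeps collecting them.

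Other sections bear on the same participant. Section 9.1 records that "some previous patients had difficulty returning to the clinic for the face-to face intervention" and offers online teaching in response. Section 11.2 describes participation "concluding with a 1-month, 3-month and 12-month follow up in person or by mail". Section 10.1 fixes the timing: "Study packets with questionnaires will be repeated approximately one-month, 3-months and 12-months after the intervention".

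On analysis, 17.1 makes the 1-month ISI primary and models it on "randomized treatment assignment, patient cancer type, the interaction between treatment assignment and cancer type, and baseline ISI level", with a permutation test. It does not say who is included or how a missing 1-month ISI is examined. Section 17.2 says "we expect a 30% drop out rate, thus a total of 158 patients will be enrolled into this study", without saying when the drop-out occurs. Section 17.3 offers reminders, and 19.1 has the statistician alerted if retention falls.

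**The concern.** Sections 20.1 and 20.3 divide people by whether they are unable or unwilling, and they treat the two groups in opposite ways. Someone who decides to skip the session is followed. Someone who cannot attend it, wear the actigraph or keep the diary is, on the wording of 20.1, taken out of the research, although that person could still return an ISI questionnaire. Randomization comes before the session is scheduled (10.1), so such a person may already belong to the randomized comparison.

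The loss would be created by the protocol itself, after randomization, and the outcome would have been obtainable. The tasks and their burdens also differ by arm. Section 21.1 foresees daytime sleepiness from the sleep curtailment that is part of BBTI, while 4.1 does not expect the control, the Healthy Eating Program (HEP), to improve sleep. Loss could therefore differ between arms, in either direction. If it does and is related to outcome, the estimate shifts, and 17.1 contains no analysis that would reveal it.

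**Working it through.** **1. The passages side by side, for a randomized participant without a completed session**

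| Situation | Governing text | 1-month ISI |
|---|---|---|
| Chooses not to attend, still answers surveys | 20.3 | collected |
| Cannot attend, could still answer surveys | 20.1 and 20.2, read literally | not collected |
| Either of these | 10.1 counts from the intervention | no defined date |

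The second row needs two conditions: that attendance is among the consent-form duties (not visible to us), and that clinic, online and home delivery all fail. The third row does not depend on the consent form.

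**2. The plan's own figures (17.2)**

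Inputs: SD 4.8, difference 3, two-sided 0.05, 55 per arm. A two-sample t-test gives 90.1% power. Inflation: 110 / 0.70 = 157.1, hence 158, or 79 per arm. The figures reproduce. The inflation protects power against 30% loss; it does not address bias.

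**3. How large a bias could be (assumed inputs)**

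If a fraction m of an arm is lost and the lost differ from completers by s points, the completer mean is off by m × s. With the same s in both arms, the bias of the contrast is (m1 − m0) × s:

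- 30% v 30%: 0 for any s.
- 35% v 25%, s = 2: 0.10 × 2 = 0.2 points.
- 40% v 20%, s = 2: 0.20 × 2 = 0.4 points.

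A simulation of the planned model agrees on scale. Assumptions: 24 of 79 lost per arm, so all 30% falls at 1 month; part of the loss in one arm only is related to worse ISI (correlation 0.3 to 0.5) and the rest is random; baseline correlation 0 to 0.5; cancer mix 40/20/20/20. Error rates are from the permutation test under no true effect; bias is from the parametric ANCOVA.

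| Outcome-related loss | Bias (ISI points) | Type I error |
|---|---|---|
| none | about 0 | 4.3% to 5.0% |
| 4 of 79, one arm | 0.13 to 0.24 | 5.1% to 6.0% |
| 8 of 79, one arm | 0.21 to 0.48 | 5.7% to 7.9% |

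With the same mechanism in both arms, bias is about 0 and error is 4.7% to 5.7% (parametric). If the loss of 8 is in HEP and the true effect is 3, the estimate falls to 2.53 to 2.78. Power then falls from 88.7% to between 77.8% and 82.5% at baseline correlation 0.

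**4. Tipping point**

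Let f = 24/79 = 0.304 be the missing share, D the observed difference and δ how much worse missing BBTI participants are than observed ones. Significance is lost when

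D − f·δ = c × √(4.8² × 2/55 + f(1 − f)δ²/79), with c about 1.98.

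For D = 3 and δ = 3.78, the left side is 3 − 1.15 = 1.85 and the right side is 1.98 × √(0.838 + 0.038) = 1.85. So δ is about 3.8 points. For D = 2.5 it is about 2.2.

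**5. Dilution from keeping people in**

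Suppose 8 per arm are regained and the 8 in BBTI gain nothing. They are 8/63 = 12.7% of the arm, so the difference becomes 3 × 55/63 = 2.62. The t-test power is 86.0% with 63 v 63, or 83.5% if only BBTI regains 8 (63 v 55). With 4 per arm it is 3 × 55/59 = 2.80 and 88.1%.

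**The case against.** The strongest reply is that 20.1 has a harmless meaning. Section 6.1 requires the ability to complete the data collection instruments, and 6.2 excludes those who cannot do so independently. If the consent-form list is about questionnaires, 20.1 removes people whose ISI could not be obtained anyway. Consent precedes the baseline week and randomization, so some 20.1 withdrawals would occur before randomization and could not bias the comparison. Section 19.2 lists adherence and accepted calls as data to review, not as grounds for removal, and 10.1 and 16.1 let participants skip items. Section 20.3 gives as its own example a person who skips the intervention and is still followed. All of this stands as evidence of intent. It does not change the wording of 20.1, which staff would have to apply.

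A reader might infer several stronger things that the documents do not support:

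- *That randomized participants are known to be lost this way.* Section 9.1 describes a difficulty that online teaching was added to solve, and 10.1 also allows home delivery. No passage shows a randomized participant who could not be reached by any route.
- *That the 30% drop-out comes from 20.1, or is all at 1 month.* Neither the cause nor the time point is given, and follow-up runs to 12 months.
- *That the primary result will be biased.* Loss that is random, or outcome-related in the same way in both arms, leaves the error rate near 5%. ANCOVA on the available cases is valid if missingness depends only on arm, baseline ISI and cancer type.
- *That the plan does not analyze as randomized.* Modeling randomized assignment with a permutation test already implies it. An explicit analysis set is mostly a matter of missing detail.

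The tipping point also gives some reassurance. At an observed 3-point difference, 24 missing BBTI participants would have to average worse than the observed HEP mean. With 12 missing per arm, the same formula gives about 8 points.

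**Conclusion.** The wording conflict between 20.1 and 20.3 is real and should be fixed. Followed as written, 20.1 changes what the trial does: it ends collection of a primary outcome that could have been obtained. The claim goes no further than that. The number affected is unknown, the direction of any bias is unknown, and at 4 of 79 in one arm the effect is little or nothing. The figures for 8 of 79 (up to about 0.5 points and 8% error) rest on assumed one-arm, outcome-related loss.

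If the consent-form list covers only questionnaires, the 20.1 point shrinks to a minor clarification. The undefined 1-month date for non-attenders and the lack of a sensitivity analysis under an expected 30% drop-out would remain. The sample size is not in error.

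**What to change.** 1. Reconcile 20.1 with 20.3: after randomization, not completing the session, diaries, actigraphy or calls does not by itself end outcome collection; withdrawn consent does. Handle falsified responses separately. This concerns outcome collection only and proposes nothing about how either program is delivered.
2. In 10.1, define the 1-month date for people who never attend, by the same rule in both arms.
3. In 17.1, state that every randomized participant with a 1-month ISI is analyzed in the assigned arm, whatever was attended.
4. Keep the permutation ANCOVA as primary and prespecify one sensitivity analysis for missing 1-month ISI. A delta-shift or tipping-point analysis is one option among several; if chosen, its range should reach about 4 ISI points, given the 3.8 above. Report withdrawals by arm, time and reason.

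The cost is a sentence in 20.1, a short addition to 10.1 and 17.1, possibly matching consent-form wording through an IRB amendment, a few more mailed packets and one extra analysis. N stays at 158. The statistical price is the dilution worked out above, which is acceptable because the estimate then describes the participants as randomized.
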